20.0 Withdrawal of Subjects

N/A: This study is not enrolling subjects. This section does not apply.

20.1 Describe anticipated circumstances under which subjects may be withdrawn from the research without their consent.

Response: The principal investigator of the study can remove a participant from the research study without their approval if for any reason he/she feels is appropriate, including

- i. Pregnancy
- ii. Developing conditions included in the exclusion criteria
- iii. Subjects decision to withdraw from the study
- iv. Severe side effects specific to study drugs
- v. Any medical condition that may place patient at risk of further complications
- vi. failure to take the medication as instructed, failure to keep your scheduled appointments,
- vii. cancellation of the study by the sponsor, or other administrative reasons.

20.2 Describe any procedures for orderly termination.

NOTE: Examples may include return of study drug, exit interview with clinician. Include whether additional follow up is recommended for safety reasons for physical or emotional health.

Response: If a subject withdraws from the research, the data collected to that point will be used toward the research finding. If applicable the subject will have to bring back any unused research drug and or device. If necessary, they will be asked to complete an end of study visit for their safety.

20.3 Describe procedures that will be followed when subjects withdraw from the research, including retention of already collected data, and partial withdrawal from procedures with continued data collection, as applicable.

Response: If a subject withdraws from the research, the data collected to that point will be used toward the research finding. If applicable the subject will have to bring back any unused research drug and or device. If necessary, they will be asked to complete an end of study visit for their safety.

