10.0 Procedures Involved

10.1 Provide a description of **all research procedures or activities** being performed and when they are performed once a subject is screened and determined to be eligible. Provide as much detail as possible.

NOTE: This should serve as a blueprint for your study and include enough detail so that another investigator could pick up your protocol and replicate the research. For studies that have multiple or complex visits or procedures, consider the addition of a schedule of events table in in your response.

Response:

Visit 1 (week 0):

Qualifying subjects will be asked to come for the visit in a fasting state (10-12 hr fasting), vitals will be done and safety labs for CBC, CMP, HbA1C, kidney function tests will be drawn and 24hr urine will be collected. Blood samples (30ml) will be collected for research endpoints. Training on administrating study drug and information about side effects and how to report any adverse events will be discussed with patients. One of the treatment arms will be administered to the patient (placebo or Exenatide extended release in a randomized fashion) and enough drug supply for 13+2 weeks will be dispensed. Other diabetes medications will be reviewed and any standard of care adjustments will be made. A 24hr urine collection container will be dispensed and patients will be instructed to come back after 13 weeks.

Visits 2, 3 and 4 (Weeks 13, 26 and 39):

Patients will come to this visit in the fasting state. Physical exam (only on visit 3) and vitals will be performed, safety labs for CBC, CMP, HbA1c, kidney function tests will be drawn and 24hr urine collected. Blood samples (30ml) will be collected for research endpoints. Other diabetes medications will be reviewed and any standard of care adjustments will be made. Study medication use compliance will be assessed and drug supply for 13+2 weeks will be dispensed. A 24hr urine collection container will be dispensed and patients will be instructed to come back after 13 weeks.

Visit 5 (Week 52): Patients will come to this visit in the fasting state. Physical exam and vitals will be performed, safety labs for CBC, CMP, HbA1c, kidney function tests will be drawn and 24hr urine collected. Blood samples (30ml) will be collected for research endpoints. Other diabetes medications will be reviewed and any standard of care adjustments will be made. Patient will be discharged from the study after the final safety phone call at week 56.

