Response Safety data (vitals, CBC, CMP, urinary markers) will be collected at screening, during and at end of the study. Injection site reactions and hypoglycemia data will be monitored and collected at every visit. Physical examination will be performed at 26 and 52 weeks visits and safety assessments performed. Pregnancy results and contraceptive adherence plan (if applicable) will be reviewed at screening, 16 and 39 and 52 weeks.

19.3 Describe any safety endpoints.

Response: N/A.

19.4 Describe how the safety information will be collected (e.g., with case report forms, at study visits, by telephone calls with participants).

Response: The safety information will be collected at the time of the participants visit, and or during telephone calls with the participant using source documents.

19.5 Describe the frequency of safety data collection.

Response: The data collection will be done at all study visits which will be at intervals of either one or two weeks depending on the number of study visit. The patients, however, will be asked to report any adverse event or safety related information via phone as soon as it occurs and it will be reviewed the same day.

19.6 Describe who will review the safety data.

Response: The principal investigator [name], PhD and co-investigators, [name] and [name] will review the data at the completion of all visits by each subject and every 3 months to assess the safety and any potential risks to the participants.

19.7 Describe the frequency or periodicity of review of cumulative safety data.

Response: Every 3 months, [name], [name] and [name] will assess the safety and any potential risks to the participants. Safety data (vitals, CBC, CMP, urinary markers) will be collected at screening, during and at end of the study. Injection site reactions and hypoglycemia data will be monitored and collected at every visit. Physical examination will be performed at 26 and 52 weeks visits and safety assessments performed. Pregnancy (if applicable) will be tested at screening, 16 and 39 and 52 weeks. Oral anti-hyperglycemic agents and/or insulin dose titration will be done to avoid hypoglycemia. Phone calls will be made for safety and compliance follow-up at least 6 time during the study. The patients, however, will be instructed to report any adverse event or safety related information via phone as soon as it occurs. All safety data will be reviewed by the PI or sub-investigators within 1-2 days of collection.

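### Section 20 permits removal from the research on grounds that may relate to treatment or renal outcome and plans no UACR afterwards, so the 1-year intention-to-treat comparison rests on an unstated missing-at-random assumption

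*Combined protocol and SAP*

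**What the plan says.** Section 20.1 of the combined protocol and SAP opens: "The principal investigator of the study can remove a participant from the research study without their approval". Its list includes "Developing conditions included in the exclusion criteria" (ground ii), severe side effects specific to the study drugs (iv), a medical condition that puts the patient at risk of further complications (v), and "failure to take the medication as instructed, failure to keep your scheduled appointments" (vi). The wording is permissive. Section 19.1 is firmer: it says that subjects will be withdrawn where risks are significant or cannot be managed, and it refers to section 20.

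Sections 20.2 and 20.3 give the same answer: "If a subject withdraws from the research, the data collected to that point will be used toward the research finding". The only later contact is conditional: "If necessary, they will be asked to complete an end of study visit for their safety". The form's prompt for 20.3 asks about "partial withdrawal from procedures with continued data collection, as applicable", and the answer does not take this up. No section describes a patient who stops study drug but stays in follow-up.

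Section 17.1 says that all analyses follow the intention-to-treat principle and that the primary analysis is an MMRM of change from baseline in albuminuria. It gives no missing-data assumption and no sensitivity analysis. Section 17.2 allows for 15% drop-out.

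**The concern.** An intention-to-treat comparison at 1 year asks how the randomised groups differ whether or not patients kept taking the drug. For that, UACR is needed from patients who stop or take the drug poorly. Section 20 permits exactly these patients to leave the research and plans no UACR for them afterwards.

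The grounds arise after randomisation, and some may be linked to arm or outcome. Severe drug-specific side effects are tied to treatment. Under section 6.3 the exclusion conditions include eGFR below 30 ml/min, so ground ii permits removal of patients whose kidneys worsen, in a trial of kidney outcome. They also include blood pressure above 160/100, while section 3.1 reports that exenatide lowers systolic pressure. If removal follows such events, the patients left with late UACR values may no longer be comparable between arms.

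**Working it through.** **Step 1: what the plan's drop-out figure covers.** Inputs from section 17.2: difference 60 mg/g, SD 91 mg/g, α 0.05 (taken as two-sided), β 0.2, 15% drop-out.

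- Per group, equal allocation: 2 × (1.960 + 0.842)² × (91/60)² = 2 × 7.85 × 2.30 = 36.1, so 37 by the normal approximation. The t distribution gives 38 (power 0.81), which is the plan's figure.
- Inflation: 2 × 38 = 76, and 76/0.85 = 89.4, rounded up to 90, as planned.
- Expected loss: 0.15 × 90 = 13.5 patients.

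The allowance makes up for the number of patients lost. It does not address who is lost or why.

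**Step 2: what removal costs in scheduled UACR values.** Section 10 schedules urine at weeks 0, 13, 26, 39 and 52, and calls at weeks 2, 8, 18, 34 and 46. (Section 17.1 names weeks 12 and 56 instead of 13 and 52. That is a separate matter; the visit schedule is used here.)

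| Removal after the call at week | Post-baseline values scheduled by then | Scheduled values lost |
|---|---|---|
| 2 | 0 | 4 |
| 8 | 0 | 4 |
| 18 | 1 | 3 |
| 34 | 2 | 2 |
| 46 | 3 | 1 |

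A patient with no post-baseline value has no change score and so contributes no response to an MMRM of change from baseline.

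**Step 3: which grounds can act when.** The first scheduled visit after week 0 is week 13, so missed study appointments cannot be a ground before then. Compliance is formally assessed at visits 2 to 4, when urine is also collected, so a removal decided there may come after that visit's UACR is already in hand. Total loss of post-baseline data is therefore mainly a matter of severe side effects, new conditions, or non-adherence reported by phone before week 13.

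**Step 4: whether the safety visit fills the gap.** Section 19.2 states: "Safety data (vitals, CBC, CMP, urinary markers) will be collected at screening, during and at end of the study". Under section 10.1, at week 0, "A 24hr urine collection container will be dispensed and patients will be instructed to come back after 13 weeks". So an early end-of-study visit might produce a urine sample. But the visit is conditional, its stated purpose is safety, section 20 does not mention UACR, and the visit is not tied to a scheduled time point. It may or may not help.

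**Step 5: what the MMRM then assumes.** With later values absent, the model treats them as if, given arm and earlier UACR, they would have followed those of patients who stayed. That is missing at random. It is doubtful here for two reasons. A patient taken off exenatide for severe side effects is projected from patients mostly still taking it. And removal for low eGFR depends on a measurement that section 17.1 does not place in the model.

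**Step 6: size.** A bias calculation needs the number removed per arm and the departure of their unseen UACR from the model's prediction. The documents give neither. The 15% is not split by cause, and section 20.1 also lists pregnancy, the patient's own decision and cancellation by the sponsor. No bias, power-loss or error-rate figure can be supported.

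**The case against.** The strongest reply is that nothing here breaks intention to treat. The MMRM analyses every randomised patient with a post-baseline value in the assigned arm, data before withdrawal are kept, and 15% loss is planned for. Removal is discretionary, the trial is double blind, and the protocol's working response to poor adherence is compliance checks and phone calls. The plan also names no estimand that would require off-drug values, and the consent pages, which are not available here, may contain follow-up terms.

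Much of this stands. A reader might infer that section 20 makes non-adherence an automatic exit, that non-adherent patients are left out of the analysis, or that every removed patient drops out of the model. The documents support none of these: section 20.1 says that the investigator can remove, no section excludes anyone from analysis for non-adherence, and pre-removal values are used. A reader might also infer a bias of known size or in favour of exenatide. The documents do not support that either: side effects could remove exenatide patients, while worsening renal function or blood pressure could remove patients from either arm.

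What the reply does not answer is that an assumption is needed for the missing 1-year values, that none is stated, and that the listed grounds make the usual one doubtful. Blinding does not make side effects or renal decline equal between arms.

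**Conclusion.** The point holds as a gap between the declared principle and the planned data collection. Section 20 permits loss of primary-endpoint data on grounds that may depend on treatment or renal outcome, and the 1-year comparison then rests on an unstated missing-at-random assumption. Up to four of the four scheduled post-baseline values are lost for a patient removed before week 13, and one to three for removal between later visits. The effect on the treatment comparison cannot be sized, its direction is unknown, and it may be zero if few or no patients are removed. This rests on reading removal from the research as ending scheduled urine collection, which is how sections 20.2 and 20.3 read, and on the consent form not saying otherwise. It should be changed, because values not collected cannot be recovered at analysis.

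**What to change.** Leave clinical decisions to stop study drug as they are, and make these changes:

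- Section 20: state that stopping study drug, or poor adherence, does not by itself end follow-up. For patients who do not withdraw consent, continue the already scheduled urine collections for UACR at weeks 13, 26, 39 and 52 where clinically appropriate. Check that the consent form agrees.
- Section 17.1: state that these values enter the primary MMRM in the randomised arm. State the missing-at-random assumption, and add one sensitivity analysis for patients who still have no data, for example imputation with a stated shift away from that assumption.
- Records and reporting: record the reason and date of each drug stop, and report missing UACR by arm and visit.

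The cost is wording in two sections, a consent-form check and modest follow-up effort. If all of the 15% loss (13.5, rounded up to 14 patients) returned for all four visits at the $80 per visit in section 25.1, payments would be 14 × 4 × $80 = $4,480. This is a ceiling, and it falls within the five visits per patient already planned. Assay costs are not given.

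There are two drawbacks. Little may be recovered from patients who miss appointments. And off-drug values may dilute the estimated effect, which can offset the gain in patients observed. That dilution is part of what an intention-to-treat comparison measures, but the team should accept it knowingly.

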21.0 Risks to Subjects

21.1 List the reasonably foreseeable risks, discomforts, hazards, or inconveniences to the subjects related to their participation in the research. Consider physical, psychological, social, legal, and economic risks. Include a description of the probability, magnitude, duration, and reversibility of the risks.

NOTE: Breach of confidentiality is always a risk for identifiable subject data.

Response:

All subjects will be referred to exenatide and extended release exenatide labeling safety information and discussions of the potential side effects and the different warning and precautions will take place at the time of signing the informed consent and prior to treatment.

Potential side effects of GLP-1 agonist include hypotension, nausea, vomiting and other GI side effects. Patients will be provided guidance on potential side effects and how to properly manage and report it. The potential benefits including improved glycemia, improved BP, potential renal protection, improved quality of life (QOL) will most probably overcome the potential side effects.

Exenatide extended release caused rats to develop tumors of the thyroid gland. Some of these tumors were cancer. It is not known if Exenatide extended release will cause thyroid tumors or a type of thyroid cancer called medullary thyroid cancer in people. This will be discussed in details with all participating subjects. Exenatide is contraindicated in patients with a personal or family history of MTC and in patients with Multiple Endocrine Neoplasia syndrome type 2 (MEN 2).

Injection-site reactions: Serious injection-site reactions, with or without bumps (nodules), have happened in some people who use exenatide extended release. Some of these injection-site reactions have required surgical intervention. Report any injection site reactions including nodules to study investigators.

Severe allergic reaction (anaphylaxis) to study drugs or placebo ingredients or other interventions may accrue in rare cases. Epinephrine is the primary treatment for anaphylaxis with no absolute contraindication to its use. Our site and staff are trained and equipped to assist patients with such reactions. Severe conditions that are not satisfactorily managed in site will be transferred to the hospital emergency department for further assessment and help.

All subjects will be informed of the potential complication of administration a blood draw, which includes mild bruising at the site. This should resolve in few days

Breach of confidentiality is always a risk. However, to minimize this risk patient data will be coded using a unique identification number and the data will only accessible to the study personnel.

21.2 Describe procedures performed to lessen the probability or magnitude of risks, including procedures being performed to monitor subjects for safety.

Response: Patients will be instructed to call the Diabetes Center to speak to a study investigator directly in case of any problem or untoward side effects. Pregnancy (if applicable) will be tested at screening, 16 and 39 and 52 weeks. Oral anti-hyperglycemic agents and/or insulin dose titration will be done to avoid hypoglycemia. Phone calls will be made for safety and compliance follow-up at least 6 time during the study. The patients, however, will be instructed to report any adverse event or safety related information via phone as soon as it occurs. All adverse events will be reviewed by the PI or sub-investigators within 24 hr of reporting and all safety data will reviewed every 3 months.

21.3 If applicable, indicate which procedures may have risks to the subjects that are currently unforeseeable.

Response:

Any adverse effects of Exenatide not currently known or those unique to their use in Type 2 diabetes with diabetic kidney disease may be some of the unforeseeable risks.

21.4 If applicable, indicate which research procedures may have risks to an embryo or fetus should the subject be or become pregnant.

Response: Not applicable, we will not be enrolling pregnant participants or who may become pregnant or within child bearing years without signing the consent stating they will use at least two forms of birth control. If a participant becomes pregnant they will be withdrawn from the study immediately.

21.5 If applicable, describe risks to others who are not subjects.

Response: Not applicable, there is no risk to others not participating in this study.

22.0 Potential Benefits to Subjects

22.1 Describe the potential benefits that individual subjects may experience by taking part in the research. Include the probability, magnitude, and duration of the potential benefits. Indicate if there is no direct benefit.

NOTE: Compensation **cannot** be stated as a benefit.

Response: Exenatide LR is approved for treatment of Type 2 diabetes and has beneficial effects on glycemic control and weight. Subjects will also benefit from close monitoring of their renal disease..

23.0 Compensation for Research-Related Injury

N/A: The research procedures for this study do not present risk of research related injury (e.g. survey studies, records review studies). This section does not apply.

23.1 If the research procedures carry a risk of research related injury, describe the available compensation to subjects in the event that such injury should occur.

Response: Routinely, Buffalo General Hospital, Erie County Medical Center, and/or the University at Buffalo, State University of New York, its agents, or its employees do not compensate for or provide free medical care for human subjects/participants in the event that any injury results from participation in a human research project. In the unlikely event that they become ill or injured as a direct result of participating in this study, they may receive medical care, that will be covered by study.

23.2 *Provide a copy of contract language, if any, relevant to compensation for research related injury.*

*NOTE: If the contract is not yet approved at the time of this submission, submit the current version here. If the contract is later approved with **different language regarding research related injury**, you must modify your response here and submit an amendment to the IRB for review and approval.*

Response: *AstraZeneca shall reimburse the Institution for the direct, reasonable and necessary medical expenses incurred by the Institution for the treatment of any personal injury that is a direct result of adverse drug experiences to subjects resulting directly from any manufacturing defects in the Study Drug to which the Subjects would not have been exposed but for their participation in the Study if (i) the Institutional parties have complied with this Agreement, the Protocol and any written instructions of AstraZeneca concerning the Study Drug and (ii) all the requirements of informed consent have been complied with. AstraZeneca will not provide compensation for lost wages or for any other damages, expenses or losses, or for medical expenses that have been covered by a Subject's medical or other insurance.*

24.0 Economic Burden to Subjects

24.1 *Describe any costs that subjects may be responsible for because of participation in the research.*

NOTE: Some examples include transportation or parking.

Response: All research expenses will be covered. Participants will not be subjected to any out of pocket cost.

N/A: This study is not enrolling subjects, or is limited to records review procedures only. This section does not apply.

25.0 Compensation for Participation

25.1 *Describe the amount and timing of any compensation to subjects, including monetary, course credit, or gift card compensation.*

Response:

Total compensation for this study will be up to \$400.00 after the completion of all study visits. Each completed study visit will be paid at \$80.00. There is a total of 5 study visits. This payment will be received in the form of a check to the study participant.

- N/A:** This study is not enrolling subjects, or is limited to records review procedures only. This section does not apply.
- N/A:** There is no compensation for participation. This section does not apply.

